Appendix D

Assumptions and calculations made to estimate the TRALI rate in cases and controls

Using the Finlay data and some acceptable assumptions concerning HLA prevalence among donors, then the estimate of TRALI incidence is 2.32% in the case recipient group and 0.79% in the control recipient group. A sample of 1,175 in each of the two groups will have 90% power to detect a difference in TRALI rates.

The Finlay paper gives us an estimate that 7/820 recipients will develop TRALI. However, for calculation purposes we want an estimate of the TRALI rate per component, instead of per recipient. These 820 recipients received 6,888 components, for an average of 8.4 components per recipient. Thus, another estimate is that 7/6888 components will result in TRALI.

Preliminary results from LAPS-I show about 16% of female donors are HLA positive, 1% of male donors are HLA positive, and that donors are roughly 50% female. Then we can estimate that 9% of donations are HLA positive. Components are derived from donations with no predilection towards HLA status, thus we can also then estimate that 9% of components are HLA positive.

Next, we assume most TRALI reactions are a result of an HLA positive component (literature suggests 80% of TRALI reactions implicate an HLA positive donation).

The Finlay component data consists of 51% low risk components and 49% high risk components. High risk components are assumed to be six times greater risk of causing TRALI. The overall TRALI risk of 7/6888 components can be translated into an estimate that there is a 0.18% probability of a TRALI incident per high risk component. An interim analysis is proposed to estimate this probability. If the probability is smaller than 0.18%, then increasing the sample size will be considered (see Appendix H).

Further, using the estimates that 9% of components are HLA positive and that 80% of TRALI incidents are immune mediated, then TRALI risk estimates conditional on HLA status of the component can be derived. If the HLA status of the component is positive, then the probability a high risk component causes a TRALI reaction is 1.59%. If the HLA status of the component is negative, then the probability a high risk component causes a TRALI reaction is 0.04%.

For each HLA positive donor in the study, we consider all of this donor's components in the study period, and enroll recipients of these components as case subjects. In our case recipient group, we will know that one component is HLA positive and that any other components (the number of other components can vary for each recipient) the recipient receives have unknown HLA status. For each HLA negative donor in the study, we consider all of this donor's components in the study period, and enroll recipients of these components as control subjects. In our control group, we will know that one component is HLA negative and that any other components the recipient receives have unknown HLA status. Assume the number of components a recipient receives can be anything from 1 to 11, and averages 6. (Of minor note, the case and control groups will have a higher mean number of components than the overall recipient mean. The reason is that recipients with greater number of components have a higher chance of selection into the study, i.e. since we select components and find the recipient that

received that component, then a recipient with 11 components has 11 chances to be selected, while the recipient with a single component has just 1 chance to be selected).

Using the estimates of TRALI incidence per component (conditional on whether a component is HLA positive, HLA negative, or unknown HLA status), we can estimate the TRALI incidence per case recipient and per control recipient by first calculating the probability of not developing TRALI when receiving on average of 6 components (range 1-11), and then taking the complement of that probability to estimate the probability of the recipient developing TRALI after receiving these components. As an example, a case recipient who receives one HLA antibody-positive high risk component and two high risk components whose HLA status is unknown would have a probability of not developing TRALI equal to $(0.0159) \times (0.0018) \times (0.0018)$ and a probability of developing TRALI equal to $1-\{(0.01.59) \times (0.0018) \times (0.0018)\}$. Using this method, we estimated that the TRALI rates would be about 2.32% for case recipients and 0.79% for control recipients.

The estimate of 0.79% for control recipients is close to the Finlay estimate (0.85%=7/820) as expected. The Finlay estimate is the TRALI incidence for recipients transfused with components of unknown HLA status. Knowing that one of the transfused components is HLA negative lowers the risk slightly, while the greater average number of components in the control group raises the risk slightly, for a net negligible change in the risk. The estimate of 2.32% in case recipients is less than the composite estimate for other lookback studies (2.7%=5/184). This too is expected, as the other lookback studies only considered components from donors who had been 'implicated' in a TRALI incident.

If the average number of transfused components per recipient were 4 rather than 6, then the TRALI rate estimates in the case recipient group and control recipients groups are lowered to 2.0% per case recipient and 0.5% per control recipient. The statistical power of the study increases as average number of components decreases. Conversely, the statistical power of the study decreases as the average number of components increases. If the interim analysis finds the average to be larger than 6, then increasing the sample size will be considered (see Appendix H). A one-sided 0.05 level test with samples of 1,175 in each of the two recipient groups will have 90% power to statistically detect a greater TRALI incidence among case recipients if 6 components are transfused (statistical power computed using StatXact for an exact conditional test comparing two binomial proportions).

Appendix E: Expected participating hospitals for LAPS-II: IRB, type of medical records, and difficulty in accessing records

No.	No. Participating Hospital Name		Type of IRB (check one)			Patient records (Check one)		On a scale of 1-5 how easy is it to obtain access to medical records?				
							Very easy			Very difficult		
		Hosp	Univ	Other	Electro- nic	Paper	1	2	3	4	5	
		Но	xwort	h Bloo	d Center			1				
1	University Hospital		X		Х		X					
2	Christ Hospital	Х			Х			Х				
3	Jewish Hospital	X			Х			х				
4	Good Samaritan	X			Х			х				
	Hospital											
	The	e Institu	ite for	Transf	fusion Me	edicine						
5	UPMC Presbyterian		Х		Х			Х				
6	UPMC Shadyside		Х		Х			х				
7	Children's Hospital of Pittsburgh of UPMC		X			Х			Х			
8	UPMC Passavant		х			х			Х			
9	UPMC St. Margaret		х		х				Х			
10	Magee-Women's Hospital of UPMC		X		Х				Х			
11	UPMC McKeesport		Х			Х			Х			

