HLA antibody prevalence in blood donors*	Percent of TRALI that are antibody mediated**	Average # components per transfusion episode***	'control' r	Number required in each of 'case' and 'control' recipients arms for different power estimates		
			80%	85%	90%	
8.5%	80%	6	806	917	1067	
9.0%	80%	6	886	1007	1175	
10.0%	80%	6	1034	1178	1379	

* Results for LAPS show the HLA prevalence to be about 16% for women and about 1% for men, hence overall prevalence of HLA antibodies in units transfused in hospitals participating in LAPS-II is likely to be in the range of 8.5% to 10%.

** Approximately 80% to 85% of TRALI cases are thought to be antibody mediated. The required sample size decreases as the immune mediated percentage increases, thus conservatively 80% is used in the table.

*** Recipients receiving an apheresis component are assumed to receive no other components during the transfusion episode. Recipients receiving an FFP (or other plasmas) component are assumed to receive on average a total of 6 components during the transfusion episode, and as a worst case scenario the additional components are assumed to be high risk TRALI components.

H4. Sample size and power selected for the study: From the above table and the details provided in Appendix D, the sample size selected was 1,175 for the antibody positive components and 1,175 for the antibody negative components. This number will give 90% power to detect a TRALI rate difference between the two groups of recipients. This conservatively assumes that a transfusion episode consists of 6 components although apheresis platelet component transfusion is most often a single unit transfusion episode. The percentage of TRALI that is antibody mediated is assumed to be 80% which may also be a conservative estimate. To the above number, a 10% margin is added to account for missing records etc. Therefore, the total number of antibody positive and antibody negative components is 1,295 for each group.

Based on OSMB recommendations we plan to conduct an interim analysis to see if the estimated sample size is adequate. The interim analysis will assess the average number of components per transfusion episode (assumed to be 6) and the TRALI incidence per component of unknown HLA status (assumed to be 0.18%). If the average is much greater than 6 or the incidence much lower than 0.18%, then increasing the sample size will be considered. A detailed description of the interim analysis is provided in Appendix H.

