Appendix H: Interim Analysis

The statistical power for the study is based on several assumptions, including the estimated incidence of TRALI/Possible TRALI. Other assumptions include the number of units transfused per transfusion episode. Although these assumptions are based on validated processes, such as, the published literature and the pilot data generated during the design of LAPSII, there remains a small possibility that the actual data may not show the expected incidence of TRALI in the two groups under study. Therefore, an internal pilot study will be performed to re-assess sample size (Tim Friede and Meinhard Kieser. 2004. Sample size recalculation for binary data in internal pilot study designs, Pharmaceutical Statistics, vol 3 p269-279).

The internal pilot study will result in an interim analysis. The interim analysis will be performed when the recipient record review process has been completed (including the review by the Medical Board) for 33% of subjects. At this juncture, the incidence of TRALI (including possible TRALI) will be calculated without un-blinding cases and controls. The internal pilot study data will allow improved estimates of TRALI incidence, and component distribution per transfusion episode to be computed. The sample size calculation as described in section H.4.will be re-done.

If the interim analysis suggests that an increase in the number of study recipients is needed, then two potential approaches are available. First approach will explore the possibility of completing the study with the larger sample size. The second approach will explore the possibility of reducing the power of the study, e.g., from 90% to 85% to reduce the degree of increase in sample size so that the increase in the number is not overwhelming. The use of internal pilot study data to re-assess sample size may have a modest effect on statistical power (A.L. Gould and W.J. Shih. 1998. Modifying the design of ongoing trials without unblinding, Statistics in Medicine, vol 17, p89-100). Therefore, reducing power to a nominal 85% may result in the effective power being on the order of 80%. In any event, changing the sample size will not affect type I error (i.e. 0.05 level test for analysis), as the sample size re-assessment will maintain blinding.

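### The interim benchmark of 6 components is the mean over all plasma recipients, but the interim averages study recipients, for whom the plan itself implies about 7

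*Protocol*

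**What the plan says.** Appendix D sets the planning assumption: "Assume the number of components a recipient receives can be anything from 1 to 11, and averages 6". A bracketed remark, described there as minor, adds that "the case and control groups will have a higher mean number of components than the overall recipient mean", the reason being that "a recipient with 11 components has 11 chances to be selected" while a one-component recipient has a single chance. Appendix D later uses this higher mean to explain why the control rate stays close to the published per-recipient estimate.

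The interim criterion appears twice. Appendix D has: "If the interim analysis finds the average to be larger than 6, then increasing the sample size will be considered". Section H4 has: "If the average is much greater than 6 or the incidence much lower than 0.18%, then increasing the sample size will be considered". Appendix H places the interim after record review, including Medical Board review, is complete for 33% of subjects. It provides for blinded estimates of TRALI incidence and of the component distribution per episode, and for the H4 calculation to be repeated.

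H3 and the footnote to Table-12 apply the 6 to plasma episodes and assume one component for apheresis platelet episodes. H3 puts the mix of high-risk components at 70% plasma and 30% apheresis.

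**The concern.** The 6 describes recipients in general. The interim can only observe study recipients, and Appendix D says that "recipients with greater number of components have a higher chance of selection into the study". An average taken from the second group is compared with a value that belongs to the first.

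The comparison guards the sample size. If 1,175 per group was derived from the higher, size-biased mean, an observed plasma average between 6 and that mean would meet the Appendix D criterion although the study is at plan or better. Two further matters are left open: whether the average covers plasma recipients only or all study recipients, and whether the observed counts would enter the repeated calculation as they stand or as a population distribution to be size-biased again.

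**Working it through.** **Inputs.** Mean 6 on a range of 1 to 11 (Appendix D). TRALI probability per high-risk component: 1.59% antibody-positive, 0.04% antibody-negative, 0.18% unknown status (H3, Appendix D). Mix 70% plasma and 30% apheresis, apheresis episodes of one unit (H3, Table-12 footnote). One-sided 0.05, exact conditional test, 1,175 per group (Appendix D). The shape of the 1-to-11 distribution is not stated, so a symmetric triangular and a uniform shape are both tried as assumptions.

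**Step 1: the plan's power.** Exact Fisher power by enumeration at 2.32% v 0.79% with 1,175 per group is 90.0%, as stated. The 85% and 80% entries in the 9% row of Table-12 (1,007 and 886) also reproduce.

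**Step 2: the mean implied by the plan's own control rate.** To first order, control rate = 0.04% + 0.7 × m × 0.18%, where m is the mean number of other components per plasma study recipient. So m = (0.79 − 0.04)/(0.7 × 0.18) = 0.75/0.126 = 5.95, or about 7 components including the study unit. This step needs no distribution shape.

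**Step 3: the size-biased mean.** When recipients are selected in proportion to their count K, the mean is E[K²]/E[K] = 6 + Var(K)/6.
- Triangular on 1 to 11: Var = 5.83, so 6 + 0.97 = 6.97.
- Uniform on 1 to 11: Var = 10, so 6 + 1.67 = 7.67.

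Any distribution with some spread gives more than 6.

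**Step 4: which mean lies behind the planned rates.** The rate for a plasma recipient with k components is 1 − (1 − p)(1 − 0.0018)^(k−1), where p is the risk of the study unit. This is averaged over k and mixed 70/30 with single-unit apheresis recipients.

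| Distribution | Mean, plasma study recipients | Case rate | Control rate |
|---|---|---|---|
| Stated in Appendix D | not stated | 2.32% | 0.79% |
| Triangular, no size bias | 6.00 | 2.21% | 0.67% |
| Triangular, size-biased | 6.97 | 2.33% | 0.79% |
| Uniform, size-biased | 7.67 | 2.41% | 0.87% |

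At a mean of 4, the size-biased triangular model gives 2.04% and 0.50%, in line with the 2.0% and 0.5% in Appendix D. Without size bias it gives 1.96% and 0.42%. The planned rates therefore already carry the size bias.

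**Step 5: the criterion under the plan.** In plasma study recipients the expected interim average is about 7, so a threshold of 6 is expected to be exceeded with no departure from plan. Pooled over all study recipients, the expected average is 0.7 × 6.97 + 0.3 × 1 = 5.18 (triangular) or 0.7 × 7.67 + 0.3 × 1 = 5.67 (uniform), below 6. A pooled average would pass 6 only once the plasma mean exceeded (6 − 0.3)/0.7 = 8.14.

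**Step 6: a second size-bias step.** Size-biasing the triangular study-recipient distribution again gives a mean of 7.67, rates of 2.41% and 0.88%, power of 88.6% at 1,175, and about 1,235 per group for 90% power. 1,235/1,175 = 1.05.

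**The case against.** The strongest reply is that neither passage is a decision rule. Both say only that an increase will be considered, and H4, the main sample-size section, asks for an average well above 6, which a value near 7 need not satisfy. The operative step is the repeated calculation in Appendix H. If the observed study-recipient distribution is used there directly, it shows that no increase is needed. The authors knew of the size bias and built it into the rates. Type I error is not at issue, because the reassessment is blinded, and Appendix H regards a 20 to 40% increase as possibly achievable.

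Most of this stands, and it limits the consequence. A reader might infer that the criterion by itself enlarges the study, or that the recalculation will count the size bias twice. The documents support neither: the action is consideration, and no passage prescribes a second size-bias step. A reader might also take the observed average to be very precise. However, the Screening Form has no field for the component count. Section K of the extended form has one, but that form is completed in full only after the x-ray and hypoxemia steps, for about 311 of 2,590 recipients (12%). Nor does the spread in Table-11 support weighting by hospital type: its counts are per admission, and H3 itself adjusts them for platelet pooling and for multiple episodes.

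The reply leaves the mismatch in place. H4's looser wording conflicts with Appendix D's and is itself undefined, and neither section says which recipients the average covers.

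**Conclusion.** The benchmark is wrong as written. The 6 is the assumed mean over all plasma recipients, while the sample size it guards rests on about 7 in plasma study recipients. Under Appendix D's wording, applied to the plasma recipients for whom 6 was assumed, the criterion is expected to be met when the plan is exactly right.

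The size is modest: an unneeded sample-size discussion and, only if the counts were size-biased a second time, an increase of about 5% (roughly 1,235 per group). If apheresis recipients were pooled in, the planned value would be about 5.2 to 5.7 and the threshold would be too lax instead. H3 ties the 6 to plasma episodes, so the pooled reading is the less natural one, but it is not excluded.

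The direction holds for any non-degenerate distribution. The value 6.97 rests on the assumed triangular shape. That shape reproduces the stated rates at means of 6 and 4, and the control-rate calculation gives about 7 without it. Power and type I error of the study as planned are not in question.

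**What to change.** In H4, Appendix D and Appendix H:

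1. Define the interim average as components per transfusion episode among plasma study recipients.
2. Compare it with the size-biased mean behind 2.32% and 0.79% (about 7), or weight each recipient's count by 1/N, where N is that recipient's number of components, and compare the weighted mean with 6.
3. State that the observed study-recipient distribution enters the repeated calculation directly, with no further size-bias step.
4. Use one criterion in Appendix D and H4, with a stated margin in place of the two present wordings.

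The cost is a few sentences and, if chosen, a simple weighting step. There is one practical requirement: episode counts must be available for an unselected set of plasma study recipients, not only for those who reach the extended form. Section K of that form covers 24 hours either side of the transfusion, whereas H3 separates episodes by a six-hour gap, so the count would also have to be taken on the episode definition.

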Appendix F: Screening Form

LEUKOCYTE ANTIBODIES PREVALENCE STUDY – PHASE II SCREENING FORM

STUDY ID LAREL

SECTION A: HOSPITAL Tx SERVICE FORM [completed by hospital Tx service staff]

DATE:				COMPL	COMPLETED BY:						
BUI#:	ТҮРЕ С		OF COM	COMP:			Tx UN	IT #:			
DATE OF ISSUE:				TIME OF ISSUE: (Military Time)							
HOSPITA	L:										
	SERVICE ISSUED TO (Record if information is available. See Note 1): (Med, Surg, Ob/Gyn, Heme/Onc, OutPt, OR, ICU, Recovery, etc.)										
PATIENT (Last, First, N			MED REC #:								
BIRTHDA	TE:				GEN	IDER:	MAI	LE 🗌	FE	MALE	
PATIENT (Check one)	AB0/RH:	[0+	0-	A+ □	A-		B+	B-	AB+	AB-
Tx REACT	TION:	`	YES 🗌	NO 🗌							
TYPE OF ((Describe):	REACTIO	N									

SECTION B: HOSPITAL FORM [completed by Med Tech/ Coordinator]

DATE:			ABSTRACTED BY:						
SOURCE OF INFORMATION:									
ELECTRONIC RADIOLOGY REPORTS DATABASE									
ELECTRONIC MEDICA	L RECO	ORDS INCLUDING	G RADIOLOGY REPOR	rs 🗌					
PAPER MEDICAL REC	ORDS								
OTHER (SPECIFY)									
			DATE	TIME (Military Time. See Note 2.)					
PRE Tx CHEST X-RAY (If yes, record date & time of up to 3 X-rays)		YES 🗌 NO [
POST Tx CHEST X-F (If yes, record date & of up to 3 X-rays)		YES 🗌 NO [

DISCHARGE DIAGNOSIS (If electronically available): List up to 10 diagnosis Assign ICD-codes	DESCRIPTIVE DIAGNOSIS	ICD CODE
1.		
2.		
3.		
4.		
5.		
6.		
7.		
8.		
9.		
10.		

If NO post transfusion chest X-ray within 24 hrs of issue of blood product then end now

PRE TRANSFUSION CHEST X-RAY REPORT: (Please write complete report. If more than one, include all reports.)

POST TRANSFUSION CHEST X-RAY REPORT: (Please write complete report. If more than one, include all reports)

SECTION C: PI REVIEW FORM [completed by PI or designee nurse/MD]

DATE OF REVIEW:		REVIEWED BY:						
EXTENDED CHART REVIEW:		YES NO						
BILATERAL LUNG INFILTRATES	NARY EDEMA	ARDS						
YES 🗌 NO 🗌	YES 🗌	NO 🗌	YES 🗌	NO 🗌				
WORSENING PULMONARY EDEMA	1	NEW PULMONARY EDEMA						
YES 🗌 NO 🗌		YES D NO D						
PI RECCOMMENDATION: Proceed	with cha	art review?	YES 🗌	NO 🗌				
COMMENTS:								

If NO extended chart review required then end now ENTER FORM DATA IN SMS. DO NOT ENTER DATA SHADED IN YELLOW.

NOTES:

- 1. Service to which the product was issued from the blood bank may not always be available. For those products issued to the operating room (OR) or the recovery room, note that the issue time may differ significantly from the transfusion time since these locations may have temporary storage facility.
- **2.** Record the date and time which is nearest to the time of study unit transfusion if there is more than one chest X-ray taken within 24 hrs prior and 24 hrs after the study unit transfusion

Appendix G: Extended Data Collection Form LEUKOCYTE ANTIBODIES PREVALENCE STUDY – PHASE II EXTENDED DATA COLLECTION FORM

Please refer to clinical information from daily chart notes, laboratory test results, radiology reports, echocardiogram reports, discharge summary, nursing notes, blood bank issue and transfusion forms and other chart records to complete this form.

SECTION A: GENERAL INFORMATION

DATE:		ABSTRACTED BY	:						
SOURCE O	SOURCE OF INFORMATION: (Check all that apply)								
ELECTRONIC RADIOLOGY REPORTS DATABASE									
ELECTRON	ELECTRONIC MEDICAL RECORDS INCLUDING RADIOLOGY REPORTS								
PAPER MEDICAL RECORDS									
OTHER (SPECIFY)									
BUI #	BUI #								
		ED EVIDENCE THAT INDEX BLOOD RANSFUSED?	YES Stop data collection	NO Continue					

SECTION B: ADMISSION & DISCHARGE

			DATE	Т	IME (Military)		
HOSPITAL	ADMISSION DISCHARGE						
HUSPITAL				(when available)		
ICU	ADMISSIC	ON					
100	DISCHARGE						
DISCHARGE ST	FATUS	ALI	VE DECEASED				
DISCHARGE D codes. Collect onl	IAGNOSIS L y if NOT prev	.ist up viously	to 10 diagnosis and assigneed in Screening For	0 10 diagnosis and assign ICDDESCRIPTIentered in Screening FormDIAGNOSIS			
				1.			
				2.			
			3.				
				4.			
				5.			
				6.			
				7.			
				8.			
				9.			
				10.			

SECTION C: PATIENT DEMOGRAPHICS

AGE					GENDER	MALE	FEMALE
WEIGHT	HT UNIT			HEIGHT	UNIT		
RACE/ETH	w	B	H	A	Other		

SECTION D: TRANSFUSION ADMINISTRATION

DATE OF Tx:			тім	TIME OF Tx:				AM		РМ	
	List BUI numbers of all involved products and their ABO/Rh type (within 6 hours prior to the onset of reaction):										
BUI #	UI # ABO/Rh			#	ABO/	BO/Rh BUI #		ABO/RI)/Rh	
								-			
VITAL SIGNS (See Note 1) BP (mm		BP (mm	Hg) PULSE/MIN		/MIN	R	RESP/MIN		TEMP (degree F)		
BEFORE Tx:											
1/2 HR DURIN	G:										
1 HR DURING	6 :										
2 HR DURING	; :										
AT COMPLETI OF Tx:	ON										
TX REACTION: (Within 6 hrs of completion of unit)		pletion of	YES			-	REPORTED TO BLOOD BANK:		YES 🗌 NO 🗌]
TYPE OF REACTION: (Describe) See Note 2											

SECTION E: HYPOXEMIA EXCLUSION CRITERIA

Concentrate the chart review process around the time window of 24 hours prior and 24 hours after transfusion of study unit. Please complete respiratory status within **six hours** of completion of the transfusion.

Estimate FiO2 as follows, if patient is receiving oxygen by nasal cannula or mask.

Room air: 0.21	1 Liter of O2: 0.23	2 Liters of O2: 0.25	3 Liters of O2: 0.27
4 Liters of O2: 0.30	5 Liters of O2: 0.35	6, 7 Liters of O2: 0.40	8, 9, 10 Liters of O2: 0.49

If receiving oxygen therapy with mechanical ventilation, use percent oxygen recorded on the patient's respiratory care data. Review ventilator data to find FiO2 value (eg. 405 oxygen administration equals a FiO2 of 0.4).

RESPIRATORY STATUS	YES	NO	NR
Oxygen saturation (SpO2) less than 90% by pulse oxymetry without oxygen therapy?			
Oxygen saturation (SpO2) less than 90% by pulse oxymetry while receiving oxygen therapy			
Ratio of SpO2/FiO2 <315 (See Note 1)			
Ratio of PaO2/FiO2 <300 (PaO2 = oxygen saturation on arterial blood gas analysis) (See Note 2)			

If answer to **ANY** of the above respiratory status items is **YES** then further chart review is required. If answer to **ALL** of the above respiratory status items is **NO** then stop now and send copy of form to Westat.

NO.	ITEM	YES	NO	NR	START DATE (If applicable)	RESOLVE DATE (If applicable)	NOTES
1	Acute CNS Injury (within 7 days before Tx)				applicable)	applicable)	Note 3
2	Acute renal failure (within 7 days before Tx)						Note 4
3	Aspiration						Note 5
4	Bone marrow stem cell transplant in past 12 months						
5	Burn as an admitting diagnosis (if within 48 hrs before reaction)						
6	Cancer or recent (within 1 month) chemotherapy						
7	Cardiac bypass during current admission (within 48 hrs before reaction)						
8	Cardiac ischemia during current admission (within 7 days before Tx)						
9	Hx of chronic alcohol abuse						Note 6
10	Hx of chronic renal failure						Note 7
11	Congestive heart failure during current admission (within 7 days before Tx)						Note 8
12	Hx of coronary artery disease						
13	Hx of diabetes mellitus						Note 9
14	DIC during current admission (within 7 days before Tx)						Note 10
15	Drug overdose as admitting diagnosis (within 48 hrs before reaction)						
16	Exposure to high altitude as admitting diagnosis (within 48 hrs before reaction)						
17	Heat stroke as admitting diagnosis (within 48 hrs before reaction)						
18	Hemorrhagic shock during current admission (within 48 hrs before reaction)						
19	High INR (>3.0) during current admission (within 7 days before Tx)						
20	Hx of immunosuppression						
21	Just underwent surgery (within 48 hours)						

SECTION F: PATIENT HISTORY & CLINICAL FINDINGS
NO.	ITEM	YES	NO	NR	NOTES
22	Hx of leukemia or lymphoma				
23	Lung contusion during current admission (if diagnosis made within 48 hrs before reaction)				Note 11
24	Lung radiation in previous six months				
25	Multiple fractures during current admission (Within 7 days before Tx)				
26	Near drowning as reason for admission (within 48 hrs before reaction)				
27	Hx of chronic obstructive lung disease				
28	Acute pancreatitis during current admission (within 7 days before Tx)				Note 12
29	Rapid resolution of lung infiltrates on chest x-ray				If within 6 hrs with diuresis/ dialysis
30	Receiving amiodarone during current admission (within 48 hrs before reaction)				
31	Hx of restrictive lung disease				
32	Hx of severe liver disease				Note 13
33	Symptomatic anemia during current admission (within 48 hrs before reaction)				Note 14
34	Upper airway obstruction during current admission (within 48 hrs before reaction)				

SECTION G: OTHER CLINICAL FINDINGS

NO.	ITEM	YES	NO	NR	VALU E	DATE	TIME (military)	NOTES
1	Dialysis within 7 days before the study unit Tx (Hemo or Peritoneal)							
2	Dialysis within 7 days after the study unit Tx (Hemo or Peritoneal)							
3	Extubation (within 24 hrs before reaction)							Note 15
4	FiO2 (highest value) in 24 hrs before Tx of study unit							
5	FiO2 (highest value) in 24 hrs after Tx of study unit							
6	Fluid balance – Excess fluid 24 hrs before Tx of study unit (mL)							Note 16
7	Intubation within 24 hrs before Tx of study unit							
8	Intubation within 24 hrs after Tx of study unit							

9	Invasive procedure: Central line placement within 24 hrs before Tx.							
---	---	--	--	--	--	--	--	--

NO.	ITEM	YES	NO	NR	VALU E	DATE	TIME (military)	NOTES
10	Invasive procedure: Liver biopsy							
11	Invasive procedure: Lumbar puncture (within 24 hrs before Tx.)							
12	Invasive procedure: Other (within 24 hrs before Tx.) Specify							
13	Mechanical ventilation within 24 hrs before study unit Tx							
14	List all medications given to the	patient w	ithin 2	4 hrs p	rior to trans	fusion:		

NO.	ITEM	PROCEDUR	E	DATE	TIME (military)	NOTES
		Nasal Cannula				
15		Face Mask				
	Oxygen administration method within 24 hrs before Tx of study unit	СРАР				
		Intubation				
		Other				
		Nasal Cannula				
		Face Mask				
16	Oxygen administration method within 24 hrs after Tx of study unit	СРАР				
		Intubation				
		Other				

SECTION H: PRE-TRANSFUSION EVENTS

NO.	ITEM	YES	NO	NR	START DATE	RESOLVE DATE	NOTES
1	Pre-transfusion fever within 24 hrs before Tx (temp above 100.4F or 38C)				(If applicable)	(If applicable)	
2	Pre-transfusion chills without fever within 24 hrs before Tx						
3	Pre-transfusion bacterial sepsis within 24 hrs before Tx						Note 17
4	Pre-transfusion shortness of breath/dyspnea within 24 hrs before study unit Tx						
5	Pre-transfusion hypotension (systolic BP <90 mmHg) within 24 hrs before study unit Tx						
6	Pre-transfusion hypertension (systolic BP >140 mmHg) within 24 hrs before study unit Tx						
7	Pre-transfusion shock within 24 hrs before study unit Tx						Note 18
8	Pre-transfusion O2 sat <90% on pulse oxymetry (SpO2) with or without O2 administration within 6 hrs before Tx						
9	Ratio of SpO2/FiO2 <315 within 6 hrs prior to Tx						Note 19
10	Pre-transfusion arterial blood gases within 6 hours prior to tx showing pO2/FiO2 <300 mm Hg						Note 20
11	Pre-transfusion lung auscultation reveals rales(crackles) within 24 hrs before study unit Tx						
12	Pre-transfusion lung auscultation reveals rhonchi within 24 hrs before study unit Tx						
13	Pre-transfusion elevated jugular venous pressure within 24 hrs before study unit Tx						
14	Pre-transfusion hepatojugular reflux detected within 24 hrs before study unit Tx						
15	Pre-transfusion cyanosis						
16	Pre-transfusion central venous catheter measured elevated central venous pressure (>8 mm Hg) within 6 hrs before Tx						
17	Pre-transfusion central catheter measured elevated pulmonary artery wedge pressure (>20 mm Hg) within 6 hrs before Tx						
18	Pre-transfusion peripheral pitting edema detected within 24 hrs before study unit Tx						
19	Pre-transfusion diagnosis with ARDS within 24 hrs before study unit Tx						From MR or chest X-ray report
20	Pre-transfusion, patient required ICU admission within 24 hrs before study unit Tx						
21	Pre-transfusion, required vasopressures to support blood pressure within 24 hrs before study unit Tx (e.g., dopamine, norepinephrine, epinephrine)						

SECTION I: VITAL SIGNS AFTER TRANSFUSION REACTION

Record 3 vital signs that were 6 -8 hrs apart. Leave blank if no transfusion reaction is noted in the medical record or reported to the blood bank.

VITAI	VITAL SIGNS AFTER TRANSFUSION REACTION: (Note 21)										
NO.	DATE	TIME (military)	BP (mmHg)	PULSE/MIN	RESP/MIN	TEMP (degree F)					
1											
2											
3											

SECTION J: POST TRANSFUSION EVENTS

NO.	ITEM	YES	NO	NR	NOTES
1	Post-transfusion fever ((temp above 100.4F or 38C) within 6 hrs				
2	Post-transfusion chills within 6 hrs without fever				
3	Acute hemolytic transfusion reactions within 24 hrs				
4	Delayed hemolytic transfusion reaction within 7 days				
5	Minor allergic (skin rash) within 6 hrs				
6	Severe allergic (anaphylactic) within 6 hrs				
7	Post-transfusion bacterial sepsis within 24 hrs				
8	Cardiac/fluid overload or congestive heart failure within 6 hrs				
9	Post-transfusion shortness of breath/dyspnea within 6 hrs				
10	Post-transfusion hypotension (systolic BP <90 mmHg) within 6 hrs				
11	Post-transfusion hypertension (systolic BP >140 mmHg) within 6 hrs				
12	Post-transfusion shock				
13	Post-transfusion O2 sat <90% on pulse oxymetry (SpO2) with or without O2 administration within 6 hrs				
14	Post transfusion ratio of SpO2/FiO2 <315 within 6 hrs				
15	Post-transfusion arterial blood gases within 6 hours after completion of transfusion showing pO2/FiO2 <300 mm Hg				
16	Post-transfusion lung auscultation reveals rales(crackles) within 24 hrs				
17	Post-transfusion lung auscultation reveals rhonchi within 24 hrs				
18	Post-transfusion elevated jugular venous pressure within 6 hrs				
19	Post-transfusion hepatojugular reflux detected within 6 hrs				

NO.	ITEM	YES	NO	NR	NOTES
20	Post-transfusion cyanosis within 6 hrs				
21	Post-transfusion central venous catheter measured elevated central venous pressure (>8 mm Hg) within 6 hrs				
22	Post-transfusion central catheter measured elevated pulmonary artery wedge pressure (>20 mm Hg) within 6 hrs				
23	Post-transfusion peripheral pitting edema detected within 24 hrs				
24	Post-transfusion, was there a loss of 4.5 kg weight in 72 hours after diuretic treatment				Note 22
25	Clinically suspect TRALI within 6 hrs				
26	Post-transfusion diagnosis of ARDS within 24 hrs				
27	Post-transfusion, patient required ICU admission within 24 hrs				Note 23
28	Post-transfusion, required vasopressures to support blood pressure within 24 hrs (e.g., dopamine, norepinephrine, epinephrine)				
29	Rapid resolution of lung infiltrates on chest X-ray after diuresis or dialysis within 6 hrs				

SECTION K: OTHER BLOOD COMPONENTS AND FLUID ADMINISTRATION

NO.	COMPONENT/FLUID	PRE-Tx AMOUNT (24 hour before Tx of the study unit started) Record if applicable	POST-Tx AMOUNT (24 hours after the Tx of the study unit finished) Record if applicable
1	RED BLOOD CELLS (No. of Units)		
2	PLATELETS, WHOLE BLOOD (No. of units)		
3	PLATELETS, APHERESIS (No. of Units)		
4	PLASMA (No. of Units)		
5	CRYSTALLOIDS - Normal saline, Half normal saline, D5W, D5/Half Normal saline, Lactated Ringer's solution (mL)		
6	COLLOIDS - albumin, plasma protein fraction or PPF (mL)		
7	Urine output (mL)		
8	Gastric tube output (mL)		
9	Surgical drain output (mL)		
10	Fluid balance – Excess fluid (mL)		

SECTION L: ELECTROCARDIOGRAM FINDINGS

PRE-TRANSFUSION EKG REPORT (Please write complete reports in box below for all EKGs that were done within 24 hrs prior to study unit transfusion. Please write date/time for each report.)

POST-TRANSFUSION EKG REPORT (Please write complete reports in box below for all EKGs that were done within 24 hrs after study unit transfusion. Please write date/time for each report.)

SECTION M: ECHOCARDIOGRAM FINDINGS (M-MODE & 2-D)

PRE-TRANSFUSION ECG WRITTEN REPORT (Please write complete report in box below; if more than one report, include all reports. Please write date/time for each report.)

POST-TRANSFUSION ECG WRITTEN REPORT (Please write complete report in box below; if more than one report, include all reports. Please write date/time for each report.)

SECTION N: LABORATORY FORM

COM	PLETE BLOOD COUNT	[
NO.	PARAMETER	PRE-Tx (Most recent within 24 hrs. Record if applicable)			POST-Tx (Most recent within 24 hrs. Record if applicable)		
		DATE	TIME (military)	VALU E	DAT E	TIME (military)	VALU E
1	Hemoglobin gm/dL						
2	Hematocrit (%)						
3	Total WBC x 10 ³ /uL						
4	Monocytes (%)						
5	Neutrophil (%)						
6	Lymphocyte (%)						
7	Platelet count x 10 ³ /uL						

OTHER LAB RESULTS

			PRE-Tx (Most recent within 24 hrs. Record			POST-Tx		
				rs. Record		recent within		
NO.	PARAMETER	if	if applicable)			Record if applicable)		
		DATE	TIME (military)	VALUE	DATE	TIME (military)	VALUE	
1	BUN (mg/dL)							
2	Creatinine (mg/dL)							
3	CK (IU/L)							
4	CK-MB (IU/L)							
5	Troponin I (IU/L)							
6	K (mEq/L)							
7	Na (mEq/L)							
8	B-type natriuretic peptide (pg/mL)							
9	Fibrinogen level (mg/dL)							
10	Fibrin degradation, d- dimer, or split products (record value)							
11	Total bilirubin (mg/dL)							

SECTION O: ARTERIAL BLOOD GASES

Record all values within six hours of the study unit transfusion

	DATE	TIME	FiO ₂	PaO ₂	PaCO ₂	pН
PRE-Tx						
(Most recent within 6 hrs)						
POST-Tx						
Closest to time of reaction						
(Not more than 11 hrs and 59						
min after completion of Tx)						
POST-Tx						
(Earliest between 12 hrs and 23						
hrs & 59 min after completion						
of Tx)						
POST-Tx						
(Earliest between 24 hrs and 35						
hrs & 59 min after completion						
of Tx)						

SECTION P: TRIAGE MD REVIEW

DIAGNOSIS OF MODERATE TO SEVERE TACO (only if clear evidence present)	YES 🗌	NO 🗌
EXPERT REVIEW REQUIRED:	YES	NO 🗌
Digital CXR Images available	YES 🗌	NO 🗌

